5.3. Procedures for Maintaining and Breaking the Masking

Under normal circumstances, the mask should not be broken until all subjects have completed the study and the database is finalized. Otherwise, the mask should be broken only if specific emergency treatment/course of action would be dictated by knowing the treatment status of the subject. In such cases, the investigator may, in an emergency, contact the medical monitor. In the event the mask is broken, the sponsor must be informed as soon as possible. The date, time, and reason for the unmasking must be documented in the subject record. The investigator is also advised not to reveal the study treatment assignment to the clinical site or sponsor personnel.

Subjects who have had their treatment assignment unmasked are expected to return for all remaining scheduled evaluations. Subjects who are discontinued will be replaced.

6. STUDY INTERVENTION

6.1. Identity of Test Articles

The following test articles will be used in this study:

Table 2: Test Articles

5	Test	Control
Name	Investigational lubricating eye drop in a	Blink [®] Tears
	Novelia [®] bottle	
Manufacturer	Johnson and Johnson Surgical Vision	Johnson and Johnson Surgical Vision
Ingredients	Boric Acid, Sodium Borate Dehydrate, Sodium Chloride, Potassium Chloride, Calcium Chloride Hexahydrate, Polyethylene Glycol 400, Magnesium Chloride Hexahydrate, Sodium Hyaluronate, Purified water	Sodium Chlorite, Boric Acid, Sodium Borate Dehydrate, Sodium Chloride, Potassium Chloride, Calcium Chloride Hexahydrate, Polyethylene Glycol 400, Magnesium Chloride Hexahydrate, Sodium Hyaluronate, Purified water
Packaging form	Over-labeled	Over-labeled

With 116 subjects targeted to be enrolled in the study and each subjects receiving 2 units/bottles of eyedrops each; 232 units/bottles of Test or Control articles is estimated to be used in the study.

6.2. Ancillary Supplies/Products

The following solutions will be used in this study:

	Solution		
Solution name/ Description	Sclerafil [®] Preservative Free Saline Solution (or other sponsor-approved product)	Fluorescein (or other sponsor- approved product)	
Manufacturer	Bausch & Lomb	Akorn Inc.	
Preservative	None	None	
Other distinguishing items (dye, packaging, approval status, etc.)	N/A	D&C Yellow No. 8, 0.6 mg	

Table 3: Ancillary Supplies

Sodium fluorescein dye will be used for biomicroscopy, as needed. Sterile, preservative free, saline may be used in this clinical study to rinse each eye.

6.3. Administration of Test Article

Test articles will be dispensed to subjects meeting all eligibility requirements, including any dispensing requirements set forth in this clinical protocol. Subjects will be dispensed an adequate supply of test articles to complete the study. Lost or damaged test articles will be replaced at the discretion of the investigator and/or the sponsor.

6.4. Packaging and Labeling

The test articles will be packaged in bottles as the primary packaging. The test article will be overlabeled to mask the subject to the identity of the eyedrops. The test articles will be in plastic bags as the secondary packaging form. The sample study label is shown below:

> For Use in Clinical Study CR-6502 EYE DROPS CAUTION - For Investigational Use Only Use in accordance with the instructions provided Net Contents: 0.34 to 0.5 FL 0Z (10.15mL) STERILE Store at Room Temperature Sponsored by: Johnson & Johnson Surgical Vision, Inc. Irvine, CA 92618 USA LOT:C2RK02 EXP: 2023/09/30 RC: S

6.5. Storage Conditions

Test articles will be maintained at ambient temperatures at the clinical site. Test articles must be kept under secure conditions.

6.6. Collection and Storage of Samples

When possible, any test article associated with an Adverse Event and/or a Product Quality Complaint must be retained pending directions from the sponsor for potential return to JJVC.

6.7. Accountability of Test Articles

JJVC will provide the Investigator with sufficient quantities of study articles and supplies to complete the investigation. The Investigator is asked to retain all test article shipment documentation for the test article accountability records.

Test articles must be kept in a locked storage cabinet, accessible only to those assigned by the Investigator for dispensing. The Investigator may delegate this activity to authorized study site personnel listed on the Site Delegation Log. All test articles must be accounted. This includes:

- 1. What was dispensed for the subject, to use out of the office, or issued for the subject to replace appropriately between visits.
- 2. What was returned to the Investigator unused, including expired or malfunctioning product.
- 3. The number and reason for unplanned replacements.

The Investigator will collect all unused test articles from the subjects at the end of the subject's participation. Subject returned unused test articles must be separated from the clinical study inventory of un-dispensed test articles and must be labeled with the subject number and date of return. Following final reconciliation of test articles by the monitor, the Investigator or monitor will return all unused test articles to JJVC.

If there is a discrepancy between the shipment documents and the contents, contact the study monitor immediately.

JJVC CONFIDENTIAL

7. STUDY EVALUATIONS

7.1. Time and Event Schedule

Table 4: Time and Events

Visit Information	Visit 1 Screening, Baseline, Dispense Drop	Visit 2 Follow-up #1	Visit 3 Follow-up #2
Time Point	Day 0	14+/- 2 days after V1	30 +/- 2 days after V1
Estimated Visit Duration	2.5 hours	1.0 hour	1.0 hour
Statement of Informed Consent	Х		
Demographics	Х		
Medical History/Concomitant Medications	х		
Adverse Event Review		Х	Х
Compliance		Х	Х
Habitual Artificial tear Usage	Х		
Average drops applied for OD and OS	Х	X	Х
Maximum number of drops applied for OD and OS (If applicable)	х	х	х
Screening Inclusion/Exclusion Criteria	Х		
Eligibility after Screening	Х		
Entrance Distance Visual Acuity	Х	Х	Х
SROS Questionnaire	Х	X	Х
VAS Questionnaire	Х	Х	Х
PRO Questionnaire	X (If applicable)	Х	Х
Non-invasive Tear Break-up Time	Х	X	Х
Biomicroscopy	Х	Х	Х
Eligibility after Baseline	Х		
Randomization	Х		
Drop Installation	Х		
Drop Dispensing & Instructions	Х	X	
Final evaluation			Х

7.2. Detailed Study Procedures

VISIT 1

Aim for Visit 1 to occur in the afternoon (After 12 PM). The subjects must present to Visit 1 wearing their spectacles (if applicable). Subjects will be requested to bring their habitual artificial tears with them to the visit (if applicable).

	Visit 1: Screening			
Step	Procedure	Details		
1.1	Statement of Informed Consent	Each subject must read, understand, and sign the Statement of Informed Consent before being enrolled into the study. The Principal Investigator or his/her designee conducting the informed consent discussion must also sign the consent form. NOTE : The subject must be provided a signed copy of this document.		
1.2	Demographics	Record the subject's year of birth, age, gender, race, and ethnicity.		
1.3	Medical History and Concomitant Medications	Questions regarding the subject's medical history and concomitant medications.		
1.4	Artificial Tear Use	The subject will be asked about their artificial tear use		
1.5	Eligibility after Screening	All responses to Screening Inclusion Criteria questions must be answered "yes" and all responses to Exclusion Criteria must be answered "no" for the subject to be considered eligible. If subject is deemed to be ineligible after screening, proceed to Final Evaluation and complete Subject Disposition. Refraction and Biomicroscopy forms are not required.		

	Visit 1: Baseline			
Step	Procedure	Details		
1.6	Entrance Visual Acuity	Record the distance high contrast visual acuity to the nearest letter (OD, OS, and OU) with their habitual spectacle correction in place (or unaided if applicable).		
1.7	Baseline Subject Reported Ocular Symptoms	Subjects will respond to a verbal open- ended symptoms questionnaire.		
1.8	Baseline VAS	The subject will respond to the VAS questionnaire using the Kiosk portal.		
1.9	Baseline PRO questionnaires	The subject will complete the electronic questionnaires using the Kiosk portal.		
1.10	Tear Break up Time	Record the tear film stability (NIBUT), OD and OS, with a Medmont or other topographer.	NIBUT work aid (Appendix D)	
1.11	Slit Lamp Biomicroscopy	The FDA slit lamp classification scale will be used to grade the findings and determine eligibility.		

	Visit 1: Baseline			
Step	tep Procedure Details			
		If there are any Grade 3 or higher other slit-lamp findings, the subject is ineligible to continue at this time, but may return up to one additional time to determine eligibility. If discontinued a final examination must be completed.		
		If there are no slit lamp findings, and the clearance of the fluorescein needs to be expedited, preservative- free saline may be instilled.		
1.12	Expanded Sodium Fluorescein Corneal Staining	Corneal Staining Assessment (FDA grading scale) will be assessed using a more detailed scale for internal purposes only.		
1.13	Eligibility after Baseline	All responses to Inclusion Criteria questions must be answered "yes" and all responses to Exclusion Criteria questions must be answered "no" for the subject to be considered eligible.		

	Visit 1: Dispensing			
Step	Procedure	Details		
1.14	Wash out	Allow a washout of at least 5 minutes from the end of the slit-lamp exam before instilling the artificial tear		
1.15	Randomization	Subjects will be randomized to an artificial tear drop (Test or Control)		
1.16	Drop installation	The investigator will break the seal and discard the first drop.		
		The subject will instill 1 drop in both eyes (or drops can be instilled by the investigator should the subject require drop installation training).		
		The investigator should observe the subject's technique for drop instillation and recommend new techniques to improve subject safety, if necessary.		
1.17	Subject Reported Ocular Symptoms	Subjects will respond to a verbal open-ended symptoms questionnaire		
1.18	Drop Settling	Allow the drop to settle for 5 minutes		
1.19	VAS Questionnaire	The subject will respond to the VAS Questionnaire using the Kiosk portal		
1.20	PRO Questionnaire	The subject will complete the electronic questionnaires using the Kiosk portal		
1.21	Exit Visual Acuity	Record the distance high contrast visual acuity to the nearest letter (OD, OS, and OU) with their habitual spectacle correction in place (or unaided if applicable).		
1.22	Continuance	 For the subject to continue in the study, they must meet both of the following criteria: Visual acuity is 20/30 or better OD and OS Subject willing to use the drop 3-4 times a day, or as needed (up to 6 times a day) OU for 14 +/- 2 days. 		
1.23	Review of Patient Instruction Guide	The investigator will review the patient instruction guide with the subject		

	Visit 1: Dispensing			
Step	Procedure	Details		
1.24	Dispense	 The artificial tears will be dispensed for a 14 +/- 2 day dispensing period Dispense one bottle of artificial tears A patient instruction guide will be provided, and the subject will be instructed not to use other artificial tears during the dispensing period. Subjects will be scheduled for Visit 2 in 14 +/- 2 days. Subjects will be instructed to bring the dispensed bottle of artificial tears to the next visit. Subjects will be instructed not to use other artificial tears during the dispensing period. 		

VISIT 2

Aim for Visit 2 to occur in the afternoon (after 12 PM). The subjects must present to visit 2 wearing their habitual spectacles (if applicable) having used the study drop in both eyes as instructed.

Visit 2: Follow-up 1			
Step	Procedure	Details	
2.1	Adverse Events and Concomitant Medications Review	Review the subject's concomitant medications and record any changes from the previous study visit. Record any adverse events or medical history changes from the previous study visit.	
2.2	Artificial Tear Compliance	Confirm the subject used the drops as instructed and record the average and maximum number of drops used in OD and OS per day.	
2.3	Collection of study drops	This bottle will be collected by the site and discarded.	
2.4	Subject Reported Ocular Symptoms	Subjects will respond to a verbal open-ended symptoms questionnaire.	
2.5	VAS Questionnaire	The subject will respond to the VAS Questionnaire using the Kiosk portal.	
2.6	PRO Questionnaire	The subject will complete the electronic questionnaires using the Kiosk portal.	
2.7	Preference Question	The subject will complete the electronic preference questions using the Kiosk portal, if applicable.	
2.8	Visual Acuity	Record the distance high contrast visual acuity to the nearest letter (OD, OS, and OU) with their habitual spectacle correction in place (or unaided if applicable).	
2.9	Tear Break up Time	Record the tear film stability (NIBUT), OD and OS, with a Medmont or other topographer.	NIBUT work aid (Appendix D)
2.10	Slit Lamp Biomicroscopy	The FDA slit lamp classification scale will be used to grade the findings and determine eligibility. If the clearance of the fluorescein needs to be expedited, preservative-free saline may be instilled.	
2.11	Expanded Sodium Fluorescein Corneal Staining	Corneal Staining Assessment (FDA grading scale) will be assessed using a more detailed scale for internal purposes only.	
2.12	Exit Visual Acuity	Record the distance high contrast visual	

	Visit 2: Follow-up 1			
Step	Procedure	Details		
		acuity to the nearest letter (OD, OS, and OU) with their habitual spectacle correction in place (or unaided if applicable).		
2.13	Continuance	For the subject to continue in the study, they must meet both of the following criteria: • Exit Visual acuity is 20/30 or better OD and OS • Subject willing to use the drop 3-4 times a day, or as		
2.14	Dispense	 needed (up to 6 times a day) OU until Visit 3. Dispense one bottle of artificial tears The subject will be instructed not to use other artificial tears during the dispensing period. Subjects will be scheduled for Visit 3 to ensure the visit is completed 28 to 32 days after Visit 1. Subjects will be instructed to bring the dispensed bottle of artificial tears to the next visit. 		

VISIT 3

Aim for Visit 3 to occur in the afternoon (after 12 PM). The subjects must present to Visit 3 wearing their habitual spectacles (if applicable) having used the study drop in both eyes as instructed.

	Visit 3: Follow-up 2			
Step	tep Procedure Details			
3.1	Adverse Events and Concomitant Medications Review	Review the subject's concomitant medications and record any changes from the previous study visit. Record any adverse events or medical history changes from the previous study visit.		
3.2	Artificial Tear Compliance	Confirm the subject used the drops as instructed and record the average and maximum number of drops used in OD and OS per day.		
3.3	Collection of study drops	This bottle will be collected by the site and discarded.		
3.4	Subject Reported Ocular Symptoms	Subjects will respond to a verbal open-ended symptoms questionnaire.		
3.5	VAS Questionnaire	The subject will respond to the VAS Questionnaire using the Kiosk portal.		
3.6	PRO Questionnaire	The subject will complete the electronic questionnaires using the Kiosk portal.		
3.7	Preference Question	The subject will complete the electronic preference questions using the Kiosk portal, if applicable.		
3.8	Entrance Visual Acuity	Record the distance high contrast visual acuity to the nearest letter (OD, OS, and OU) with their habitual spectacle correction in place (or unaided if applicable).		

	Visit 3: Follow-up 2		
Step	Procedure	Procedure Details	
3.9	Tear Break up Time	Record the tear film stability (NIBUT), OD and OS, with a Medmont or other topographer.	NIBUT work aid (Appendix D)
3.10	Slit Lamp Biomicroscopy	The FDA slit lamp classification scale will be used to grade the findings and determine eligibility.	
		If the clearance of the fluorescein needs to be expedited, preservative-free saline may be instilled.	
3.11	Expanded Sodium Fluorescein Corneal Staining	Corneal Staining Assessment (FDA grading scale) will be assessed using a more detailed scale for internal purposes only.	

FINAL EVALUATION

The final evaluation will ordinarily take place immediately following the last scheduled follow-up visit per the study protocol. It may also take place at any point the subject discontinues the study or is terminated from the study.

	Final Evaluation		
Step	Procedure	Details	
F.1	Final Exam Form	Indicate if the subject completed the study successfully. If subject discontinued from the study, indicate the reason.	
F.2	Exit Distance Visual Acuity	Record the distance high contrast visual acuity to the nearest letter (OD, OS, and OU) with their habitual spectacle correction in place (or unaided if applicable).	
F.3	Exit Slit Lamp Biomicroscopy (for subjects that are discontinued early)	 spectacle correction in place (or unaided if applicable). FDA Slit Lamp Classification Scale will be used to grade the findings. If the clearance of the fluorescein needs to be expedited, preservative-free rewetting drops or saline may be instilled. This step is not necessary if the subject was exited due to screen failure. Note: This step is not necessary if the subject was exited due to screen failure, or if biomicroscopy was performed as part of the final follow-up visit procedures (i.e., immediately prior to the final 	

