3.2. Inclusion Criteria

Potential subjects must satisfy all of the following criteria to be enrolled in the study:

Inclusion Criteria following Screening

The subject must:

- 1. Read, understand, and sign the STATEMENT OF INFORMED CONSENT and receive a fully executed copy of the form.
- 2. Appear able and willing to adhere to the instructions set forth in this clinical protocol.
- 3. Be between 18 and 69 (inclusive) years of age at the time of screening.
- 4. Possess a wearable pair of spectacles that provide correction for distance vision and bring them to every visit (only if applicable- to the investigator's discretion).
- 5. Self-reported symptoms of ocular dryness and/or the use of artificial tears in the last 3 months.
- 6. Subjects must be non-contact lens wearers.

Inclusion Criteria at Baseline Evaluation

7. The monocular, distance visual acuity must be 20/30 or better in each eye, either unaided or best corrected.

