3.3. Exclusion Criteria

Potential subjects who meet any of the following criteria will be excluded from participating in the study:

Exclusion Criteria following Screening

The subject must not:

- 1. Be currently pregnant or lactating.
- 2. Be diabetic.
- 3. Be currently using any ocular medications or have any ocular infection of any type which may interfere with the clinical trial (at the investigator's discretion).
- 4. By self-report, have any ocular or systemic disease, allergies, infection, or use of medication that might contraindicate or interfere with the clinical trial, or otherwise compromise study endpoints, including infectious disease (e.g., hepatitis, tuberculosis), contagious immunosuppressive disease (e.g., Human Immunodeficiency Virus [HIV]), autoimmune disease (e.g., rheumatoid arthritis, Sjögren's syndrome), or history of serious mental illness or seizures. See section 9.1 for additional details regarding excluded systemic medications.
- 5. Have habitually worn rigid gas permeable (RGP) lenses, orthokeratology lenses, or hybrid lenses (e.g., SynergEyes, SoftPerm) within the past 3 months or soft contact lenses in the past 1 month.

- 6. Have participated in any pharmaceutical or medical device related clinical trial within 30 days prior to study enrollment.
- 7. Be an employee (e.g., Investigator, Coordinator, Technician) or immediate family member of an employee (including partner, child, parent, grandparent, grandchild or sibling of the employee or their spouse) of the clinical site.
- 8. Be a current habitual user of prescription medication to treat dry eye and ocular discomfort, ocular steroids, or any medication (RX or OTC), except for artificial tears that would interfere with the clinical study (at the discretion of the investigator).
- 9. Have any known allergy or sensitivity to ingredients that the investigational product may contain (e.g., Sodium Chlorite, Boric Acid, Sodium Borate Decahydrate, Sodium Chloride, Potassium Chloride, Calcium Chloride Dihydrate, Magnesium Chloride Hexahydrate, Polyethylene Glycol 400, Sodium Hyaluronate and Purified Water).

Exclusion Criteria at Baseline Evaluation

The subject must not:

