14.5. Primary Analysis

All primary and secondary analyses will be conducted on intend-to-treat (ITT) population. Because the hypotheses are testing the non-inferiority of the Test related to the Control, a sensitivity analysis for the primary and secondary hypotheses will be performed on the per-protocol (PP) population to assess the robustness the results.

Ocular Comfort (VAS) Score: Ocular Comfort scores are recorded using Visual Analogue Scale of 0 to 100.

Primary Hypotheses for Plan A or Plan B:

The null and alternative hypotheses for non-inferiority of Test relative to Control are as follows:

$$\begin{array}{l} H_0: \Delta \leq -20 \\ H_A: \Delta > -20 \end{array}$$

where Δ is the difference in mean change from baseline at 30-Day follow-up between treatment group and control group (Test minus Control).

The Ocular Comfort Scores will be analyzed for normality using the Shapiro-Wilk test. If the data is normally distributed, then Primary Analysis Plan A will be implemented. Otherwise, Primary Analysis Plan B will be implemented.

Primary Analysis Plan A (Assuming Normality)

The overall change of ocular comfort score from baseline at 30-Day follow-up will be analyzed using a linear mixed model. The subjects are the level one units, and the investigational sites are the level two units. The model will include treatment group (Test, Control) as a fixed effect, and investigational site as a random effect. Age and gender will be included in the model as covariates. The log-likelihood ratio test may be used to assess the homogeneity of the variances with respect to treatment and sites. The Kenward and Roger¹² method will be used to calculate the denominator degree of freedom.

The model for each hypothesis is:

Let y_{ij} denote the change in VAS ocular comfort score from baseline at 30-Day follow-up for the j^{th} subject from the i^{th} site (j = 1, ..., n; i = 1, 2, ..., 8). The linear mixed model will be constructed as follows:

 $y_{ii} = \beta_0 + \beta_1 \cdot BASE_{ii} + \beta_2 \cdot TRT_{ii} + \beta_3 \cdot Age_{ii} + \beta_4 \cdot Gender_{ii} + \delta_i + \epsilon_{ii},$ where

- β₀ = Intercept
 BASE_{ij} = VAS ocular comfort score at baseline for the jth subject in the ith investigational
- TRT_{ij} = treatment assigned to the j^{th} subject in the i^{th} investigational site (Test vs Control eye drop group)
- β_2 = the treatment effect of interest
- δ_i = a random effect (subject-specific intercept) term for the ith site

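### The baseline comfort score is taken with habitual-drop status undefined, and neither analysis plan uses habitual tear use: this blurs within-arm change but does not bias the randomized comparison

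*Combined protocol and SAP*

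**What the plan says.** **Who may enter.** Section 3.2, criterion 5, accepts "Self-reported symptoms of ocular dryness and/or the use of artificial tears in the last 3 months". Tear use alone is enough, and no product is named. Section 3.3, criterion 8, carries an exemption, "except for artificial tears that would interfere with the clinical study". No criterion addresses habitual users of Blink Tears, the Control.

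**How baseline is taken.** Section 7.2 aims Visit 1 at the afternoon and adds that "Subjects will be requested to bring their habitual artificial tears with them to the visit (if applicable". At step 1.4, "The subject will be asked about their artificial tear use". At step 1.8 the baseline score is collected: "The subject will respond to the VAS questionnaire using the Kiosk portal". Nothing up to that point sets or records time since the last drop. The only washout is step 1.14, "Allow a washout of at least 5 minutes from the end of the slit-lamp exam before instilling the artificial tear", and it comes after the baseline VAS. The ban on other artificial tears begins at dispensing (step 1.24).

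**Follow-up.** Visits 2 and 3 expect subjects to arrive having used the study drops. Section 10, Table 7, lists non-use on the day of a follow-up visit as a minor deviation.

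**Analysis.** Habitual use is a collected item (Table 4). Section 5.1 stratifies by site only. In section 14.5 the Plan A prose says "Age and gender will be included in the model as covariates"; its equation also contains the baseline VAS score (BASE). Plan B bootstraps the difference in mean change and states no covariate. Section 14.6 reuses both plans for quality of vision. Section 14.7 plans no analysis by tear use.

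**The concern.** The follow-up condition is defined and the baseline condition is not. For a current tear user, Day-30 change may be on-drop minus on-drop. For a non-user it is on-drop minus untreated. One endpoint then carries two meanings, in proportions that the documents do not give.

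Three things are at stake. The mean change in each arm cannot be read as relief from an untreated state. Habitual use adds some variance to the change score. And a habitual Blink Tears user allocated to Control simply continues the same product. Section 5.2 says that the bottles differ in shape and that only an over-label hides identity, so such a subject might recognise the bottle while scoring a subjective endpoint.

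**Working it through.** **1. The plan's own sample size.** Inputs (section 14.2): margin −20, true difference 0, power 90%, SD 25/30/35. With one-sided alpha 0.025 and the noncentral t, n per arm is 34/49/66, which matches Table 9. Multiplying by π/3 for the Wilcoxon test and rounding up gives 36/52/70, which matches Table 10. For SD 30, 52/0.9 = 57.8, so 58 per arm and 116 in total. The stated figure reproduces.

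**2. Does the mixture bias the comparison?** Let U = 1 for a subject scored on their own drops, d the lift this gives to the baseline score, and p the share of such subjects. Then

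change = Y30 − (B0 + d·U), with arm mean E[Y30] − E[B0] − d·p.

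U is fixed before randomization, so p is the same in both arms in expectation and d·p cancels in Test minus Control. A simulation agrees. It used 4,000 trials, 52 per arm, p = 50% and d = 20, with an assumed untreated baseline of mean 50 and SD 20, and Day-30 score = 45 + 0.4 × untreated baseline + noise of SD 22. Monte Carlo error is about 0.1.

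| True difference | Change score | Baseline-adjusted |
|---|---|---|
| 0 | +0.16 | +0.14 |
| −20 | −19.87 | −19.93 |

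**3. Size of the effects.** p and d are not in the documents, so a range is assumed. Formulas, starting from the planning SD of 30 and 52 per arm:

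- SD of change = √(30² + p(1−p)d²)
- fall in mean change, both arms = p·d
- 95% chance imbalance in an unadjusted difference = 1.96·d·√(2p(1−p)/52)

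For p = 0.5 and d = 20: √(900 + 100) = 31.62; fall = 10; imbalance = 1.96 × 20 × √(0.5/52) = 3.84.

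| p | d | SD | t-test power | Wilcoxon n per arm with 10% dropout | Fall in mean change | Chance imbalance |
|---|---|---|---|---|---|---|
| none | – | 30.00 | 0.920 | 58 | 0 | 0 |
| 25% | 5 | 30.08 | 0.919 | 58 | 1.25 | ±0.83 |
| 50% | 10 | 30.41 | 0.913 | 59 | 5.00 | ±1.92 |
| 50% | 20 | 31.62 | 0.891 | 64 | 10.00 | ±3.84 |
| 75% | 20 | 31.22 | 0.899 | 63 | 15.00 | ±3.33 |

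The imbalance column is the extra variance seen another way. A confidence interval for the difference already allows for it.

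**4. What each adjustment buys.** In the simulation at p = 50%, d = 20 and true difference 0, the standard error of the difference is 5.33 unadjusted, 4.42 with baseline score, and 4.39 with baseline score and user status. Baseline score removes 1 − 4.42/5.33 = 17%; user status removes a further 1 − 4.39/4.42 = 0.7%. At d = 10 the user term changes nothing of note (4.28 against 4.29). Most of the precision therefore comes from the baseline score, which Plan B omits. The exact gain depends on the assumed relation between baseline and Day 30.

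**The case against.** The strongest reply is that the hypothesis concerns only Test minus Control against −20, and that this contrast is untouched. That stands. So does the point that a baseline on usual care is a legitimate choice when two lubricants are compared; an off-drop baseline would be a different definition, not a correction.

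It is also fair that on-drop baselines are permitted, not documented. Criterion 5 speaks of use in the last 3 months, not current use. The questionnaire wording and any recall period in Appendix A are not shown, and brand may already be captured at step 1.4. The Patient Instruction Guide is provided separately and could not be checked, although section 7.2 has it reviewed at step 1.23, after the baseline score.

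Stronger readings are tempting, but the documents do not support them:

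- A reader might infer that nothing adjusts for the mixed baselines. The Plan A equation contains the baseline VAS score. What is missing is a habitual-use term, and any covariate in Plan B.
- A reader might infer that assay sensitivity is lost. The mixture precedes randomization and does not by itself reduce the contrast's ability to show a difference.
- A reader might dilute Table 8's Control change of 12.5 until its confidence interval reaches zero and call that the harm. No within-arm test against zero is planned. An uncontrolled change also contains regression to the mean and expectation, and Table 8 does not state its subjects' tear use.

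What remains is that the baseline condition is undefined, and that data already collected are not used to show whether the result holds in users, in non-users and without habitual users of the Control.

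**Conclusion.** The point holds as one of interpretation and completeness, not of validity. The randomized difference is not biased, and the sample size of 116 stands. Under the assumed ranges (25–75% users, lift 5–20 points), t-test power at 52 per arm stays between 0.919 and 0.891, against 0.920. It falls below 0.90 only at the top of the assumed lift.

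The clearer effect is on within-arm change, which falls equally in both arms by 1.25 to 15 points relative to all-untreated baselines. For scale, Table 8 gives a historical Blink Tears change of 12.5. These sizes rest entirely on the assumed share and lift.

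Possible recognition of the Control bottle by habitual Blink Tears users is an open question. Unlike the mixture, it would act after allocation and would not cancel, but the documents give no figure from which to size it. The changes are worth making because they are cheap; the point does not block the trial.

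**What to change.** 1. **Models (section 14.5, and 14.6 by reference).** Add habitual artificial-tear use at entry (yes/no, step 1.4) as a fixed effect in Plan A for the primary and secondary endpoints. Make the Plan A prose agree with its equation on baseline score. Carry the same adjustment into Plan B, for example by bootstrapping the covariate-adjusted difference. Report Day-30 change per arm and the treatment difference by user status, as a descriptive subgroup.
2. **Control-product users.** Record the brand at step 1.4, and repeat the primary analysis without habitual Blink Tears users as a sensitivity analysis.
3. **Baseline definition (section 7.2).** State whether the step 1.8 VAS is meant to be on or off habitual drops. Reconcile this with Visits 2 and 3, which subjects attend after using the study drops. Record time since the last drop at each VAS.

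Whether to require any drop-free interval is a clinical decision for the sponsor, and none is proposed here.

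Cost: item 1 is wording, on data already collected, plus one model degree of freedom. Items 2 and 3 need one or two eCRF fields and a sentence or two of text. The subgroups will be small and imprecise and should be labelled descriptive.
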